Aim 2: Does the relationship between the CG and CR differentially impact the relative acceptability (Aim 2A) and efficacy (Aim 2B) of the group vs. individually delivered intervention (i.e., moderation model)?

-We anticipate that the group intervention will be associated with higher intervention engagement rates (Hyp2A) and be more effective (Hyp2B) among spousal, relative to adult child/other family, CGs.

J. Primary Outcome Variable(s): (Define the primary outcome variable(s) used to support the study objectives (e.g. if the objective is to show that treatment A is superior to treatment B in the treatment of subjects with essential hypertension, the primary outcome variable is blood pressure measurement.) **CG burden and CG distress in response to CR dementia-related symptoms**

K. Secondary Outcome Variable(s): (Define the secondary outcome variables. Such measured variables should also include the timing of measurement.) **Overall CG mental health (VR 16)**

L. Study Design and Methods:

1. Is this a clinical trial? YES NO

1.1. If yes, what type? Check all that apply.

Phase I Phase II Phase III Phase IV

1.2. If yes, this study must be registered on Clinicaltrials.gov.

2. Design

2.1. What research methods will be used in the project? Check all that apply.

 Surveys/Questionnaires	 Interviews	 Audio Taping
 Behavioral Observations	 Chart Reviews	 Video Taping
 Focus Groups	 Randomization	 Double-Blind
 Control Group	 Placebo	 Withhold/Delay Treatment
 Specimen Collection	 Deception	 Telephone Survey
 Other (Describe)		

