2.2. Describe how randomization or other treatment assignment will be made. **Once inclusion/exclusion criteria are met, we will use a random number table that will be generated using the PROC PLAN macro in SAS v9.3 to randomly assign equal numbers of CGs to the individual TEP + individual care management, group TEP + individual care management, or UC arms. The randomization program will take into account stratification by relationship type (spouse/partner, adult child/other family). This will yield 135 CGs per arm (90 spouses/partners, 45 adult children/other family). We will enroll more spousal CGs than adult children/other family CGs because this distribution more closely reflects the demographic composition of CGs providing care for Veterans with dementia found in our preliminary work.**

2.3. For retrospective research studies, provide the "look-back" period. (e.g., December 1, 1999 through December 31, 2008.) **This is primarily a prospective study. However, for the medical chart review component of the project, data from**

Veterans' medical charts will be extracted for a period of one year prior to the CGs' 3 month research assessment date.

3. Study Duration

- 3.1. Provide the estimated length of time to enroll all subjects and complete the study. **4 years**
- 3.2. Explain the expected duration of subject participation including any follow-up. **Research assessments will be conducted at baseline and 3, 6, and 12 month followup. If randomized to a treatment arm, CGs will receive up to 3 months of care management services.**
- 3.3. Specify the projected date of completion of the proposed study. **February 2019**

4. Drug Information (If not applicable state, "Not Applicable.") Not Applicable

- 4.1. Specify if the drug or biological agent is:
 - 4.1.1. FDA approved **N/A**
 - 4.1.2. Used for off-label purposes **N/A**
 - 4.1.3. Not yet FDA approved. **N/A**
- 4.2. Include the FDA Investigational New Drug (IND) number for all non-FDA approved and off-label drugs, biological agents or nutritional supplements. If not applicable state, "Not Applicable." **N/A**
- 4.3. Provide all relevant information about the drug **N/A**
- 4.4. Explain any wash-out periods, rescue medications permitted and any type of medications not permitted while enrolled in the study. **N/A**
- 4.5. Describe blinding and un-blinding procedures. **N/A**

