1. *For further instructions refer to [VHA Directive 2005-050](#), Requirements for Conducting VA-Approved International Research Involving Human Subjects, Human Biological Specimens, or Human Data*
2. *VHA Handbook 1200.05 definition of international research - VA international research is any VA-approved research conducted at international sites (not within the United States (U.S.), its territories, or Commonwealths); any VA-approved research using either human biological specimens (identified, de-identified, or coded) or human data (identified, de-identified, or coded) originating from international sites; or any VA-approved research sending such specimens or data out of the U.S. (see par. 56). **NOTE:** For the purposes of this Handbook, research conducted at U.S. military bases, ships, or embassies is not considered international research.*

N. Study Procedure

1. Study Procedures

- 1.1. Outline all study procedures - *(If necessary, include a table or flow chart, showing the schedule of the procedures and interactions. Distinguish between interventions that are experimental and carried out for research purposes vs. those that are considered standard of care. Routine procedures that are performed solely for research purposes should also be identified.)*

A. Overview: We will conduct a prospective, longitudinal, randomized control group study. Caregivers (n=405) of Veterans with dementia will be randomly assigned to one of 3 arms (1. UC, 2. individual TEP + individual care management or, 3. group TEP + individual care management) and assessed at baseline and 3, 6, and 12 month follow-up. Each study arm will include 135 CGs. In order to examine the moderating role of CG-CR relationship type, sampling and randomization will be stratified by whether the CG is a spouse/partner or adult child/other family CG. Subjects will include CGs of Veterans with dementia who have had at least one PACT encounter in the past 6 months. The study will employ a combination of self-report survey and chart-review based data collection techniques. All intervention components and research interviews will be administered via telephone, though CGs may choose to complete research assessments using paper and pencil. Clinical patient record data will be extracted using the VA Informatics and Computing Infrastructure (VINCI).

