4.1. Include statistical power calculations and the assumptions made in making these calculations. **Power calculations were computed for Aims 1 and 2. We assumed the availability of 405 participants that are eligible and agree to participate in the study. For the purposes of the power analysis, we considered 3 outcome measures (CG distress in response to dementia symptoms (RMBPC), CG burden (ZBI), and overall CG mental wellbeing (MCS subscale of VR16)). The power analysis, conducted using PASS v12, was based on the linear mixed effects model that considers the correlation among 4 repeated measures per CG and interactions between intervention group, time and CG type. The power analysis also took into consideration the following additional factors: 1) 10% drop-out; 2) adjusted 2-sided significance level of 0.017 due to multiple outcome measures which is a conservative approach; and 3) 80% power. In Aim 1, the primary interest is the interaction effects between time and intervention group. Assuming a 0.2 standardized decline in outcome within individuals over time, a correlation of 0.75 between repeated measures within an individual, and a total sample size of 360 after 10% drop-out, the study has 80% power to detect a 0.4 effect size {or larger} between the largest and smallest effects associated with intervention groups. In Aim 2, the primary interest is to examine the impact of the CG and CR relationship on outcomes which will be modeled as a three-way interaction between time, intervention group and CG/CR relationship. The power for Aim 2 is estimated using the same assumptions as in Aim 1, but with a sample size of 180. The study has 80% power to detect an effect of 0.66 between intervention groups within one type of CG/CR relationship. From a clinical significance standpoint, an effect of 0.4 equates to a mean of 4.6 (VR16), 3.6 (NPI), and 5.2 (RMBPC) points using data (i.e., SDs) from our pilot work. Of note, prior meta-analytic work suggests that improvements of 0.4-0.5 standard deviations on measures of CG outcomes are considered *clinically meaningful* effects and indicative of "study success", regardless of statistical significance.¹⁻³ Thus, we are confident that we will have power sufficient to detect clinically meaningful effects.**

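### The Aim 2 power figure uses N=180, which matches no post-drop-out stratum of the 2:1 design, and no detectable effect is given for the planned three-way interaction

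*Combined protocol and SAP*

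**What the plan says.** Section V item 4.1 (power calculations) bases Aim 1 on "a total sample size of 360 after 10% drop-out", a within-person correlation of 0.75, two-sided alpha of 0.017 and 80% power, and reports a detectable effect of 0.4. It says the power model "considers the correlation among 4 repeated measures per CG and interactions between intervention group, time and CG type".

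For Aim 2, the same item says the effect of relationship type will be "modeled as a three-way interaction between time, intervention group and CG/CR relationship". It continues: "The power for Aim 2 is estimated using the same assumptions as in Aim 1, but with a sample size of 180". The result reported is: "The study has 80% power to detect an effect of 0.66 between intervention groups within one type of CG/CR relationship".

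Section L.2.2 (randomization) sets the stratum sizes: "This will yield 135 CGs per arm (90 spouses/partners, 45 adult children/other family"). Section I words Aim 2 as a question about the "efficacy (Aim 2B) of the group vs. individually delivered intervention", so the comparison is between the two active arms. Hypothesis 2B expects the group format to work better in spouses than in the other relatives. Section V item 4.2 plans a model with all two- and three-way interactions of relationship type, arm and time.

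**The concern.** There are two faults. First, 180 does not correspond to a stratum that the 2:1 allocation delivers once drop-out is applied, although drop-out is among the Aim 1 assumptions that Aim 2 is said to share. Second, the effect reported is a simple arm difference within one stratum, while the planned test is a difference between two such differences. The power model is said to have taken the interaction into account, but no detectable interaction is given anywhere.

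This matters because moderation shapes the design. Section N.1.1.A states: "In order to examine the moderating role of CG-CR relationship type, sampling and randomization will be stratified" by relationship type. The background section faults earlier trials for lacking power to detect moderators. With the only Aim 2 figure tied to a sample size the design does not produce and to a quantity other than the planned test, a reader cannot tell what size of moderation the trial could detect, or how to read a null interaction.

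**Working it through.** **Inputs.** Alpha 0.017 two-sided, power 80%, correlation 0.75, drop-out 10%, N=360 with 0.4 (Aim 1), N=180 with 0.66 (Aim 2), all from V.4.1; 90 and 45 per arm in three arms from L.2.2. The normal multiplier is z = 2.387 + 0.842 = 3.228.

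**1. Can the plan's figures be reproduced together?** With all assumptions unchanged, a detectable effect scales with 1/√N. Halving 360 to 180 gives 0.40 × √2 = 0.566, not 0.66. Conversely, 0.66 corresponds to N = 360 × (0.40/0.66)² ≈ 132. A three-arm F test on a single measure gives 80.6% for 0.4 at 360 if one arm differs from two equal arms, but then 92.2% for 0.66 at 180. With evenly spaced arm means it gives 81.0% for 0.66 at 180, but then 65.5% for 0.4 at 360. No variant tried gave both stated figures.

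**2. Stratum sizes after 10% drop-out.**

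| | Spouse/partner | Adult child/other |
|---|---|---|
| Three arms | 270 × 0.9 = 243 | 135 × 0.9 = 121.5 |
| Two active arms | 180 × 0.9 = 162 | 90 × 0.9 = 81 |
| Per arm | 81 | 40.5 |
| Three arms, rounded base of 360 | 240 | 120 |
| Two active arms, same base | 160 | 80 |

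None is 180. Two sources for 180 can be found: 360/2, an equal split that contradicts L.2.2, or 2 × 90 spouses in the active arms before drop-out.

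**3. Ratios of detectable effects** (same contrast, equal variance in all cells; independent of SD and correlation).
- Others to spouses: √(81/40.5) = 1.41.
- Interaction to spouses: √(1/81 + 1/40.5) / √(1/81) = 1.73.
- Interaction to others: √(1/81 + 1/40.5) / √(1/40.5) = 1.22.

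**4. Taking 0.66 at N=180 as correct.** The detectable effect is 0.66 × √(180/n), and power for 0.66 is Φ(3.228 × √(n/180) − 2.387).

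| n | Detectable effect | Power for 0.66 |
|---|---|---|
| 243 (spouses, three arms) | 0.568 | 91% |
| 121.5 (others, three arms) | 0.803 | 60% |
| 162 (spouses, two arms) | 0.696 | 75% |
| 81 (others, two arms) | 0.984 | 41% |

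**5. Calibrating to Aim 1 instead (0.4 at 360), three arms.** Spouses: 0.4 × √(360/243) = 0.487, power 98% for 0.66. Others: 0.4 × √(360/121.5) = 0.689, power 76%.

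**6. Detectable interaction, calibrated to the plan.** Multiplying the spouse figure by 1.73 gives 0.84 (from 0.487), 0.98 (from 0.568) and 1.20 (from 0.696).

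**7. Detectable interaction from SD 1 and r = 0.75.** With two active arms and no extra slope variance it is 3.228 × SD × √(2/81 + 2/40.5) = 0.879 × SD.

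| Reading | SD | Detectable interaction | Power for 0.66, others | Aim 1 power for 0.4 (120 per arm) |
|---|---|---|---|---|
| Change score | 0.707 | 0.62 | 96.5% | 97.7% |
| Linear slope, 0–12 months | 0.676 | 0.59 | 97.8% | 98.6% |
| Baseline-adjusted, one follow-up | 0.661 | 0.58 | 98.2% | 98.9% |
| Baseline-adjusted mean of three follow-ups | 0.520 | 0.46 | >99% | >99% |

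These readings are kinder to Aim 2, but they put Aim 1 power at about 98% or more, against the stated 80%. Readings that ignore change over time, with 80 and 40 per arm, give 0.88 (single measure) and 0.80 (mean of four measures).

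**The case against.** The best case for the plan is that Aim 2 compares two arms and 2 × 90 = 180 spouses exactly. Only the 360 is labelled as being after drop-out, so 180 may be an enrolled count that PASS then reduced. Even if drop-out was left out, the effect for spouses is small: 0.66 becomes 0.696 and power falls from 80% to 75%. Calibrated to Aim 1, 0.66 is conservative for spouses and only slightly optimistic for the others (0.689, 76% power). The power percentages range so widely that they cannot show 0.66 to be misleading. Finally, Section H words this purpose as exploratory, Section V item 4.2 admits that three-way models are a challenge, and nothing in the sample size, allocation or model would change.

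Much of this stands as a limit on the size of the error: 0.66 cannot be called wrong outright when the covariance structure, pattern of means and tested term are not stated. The mixed model also uses all available data, so 162 and 81 are floors.

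It does not rescue the statement. In the text, 180 replaces a post-drop-out 360, and the 2 × 90 reading leaves adult children/other family with no figure. The acknowledgement in item 4.2 supplies no number. Aim 2B remains a named aim with a directional hypothesis and its own power claim, and no reading supplies the missing interaction figure.

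**Conclusion.** The concern holds; the Aim 2 power statement should be corrected. Two things are certain from the documents: 180 is not a post-drop-out stratum of the 2:1 design, whether two or three arms are counted, and no detectable effect is reported for the planned interaction. The ratios 1.41, 1.73 and 1.22 hold for any common SD and correlation, given equal variance in all cells.

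The size of the power error is not certain. For an effect of 0.66 in the smaller stratum, power runs from 41% to over 99% depending on how the unstated PASS settings are read. The detectable interaction runs from about 0.84–1.20 SD (calibrated to the plan's own two statements) down to about 0.46–0.62 SD (SD 1, r = 0.75, change or baseline-adjusted analysis). Type I error and the planned estimates are unaffected. What is affected is whether an Aim 2 result, above all a null one, can be interpreted.

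**What to change.** Re-run PASS in Section V item 4.1 on the actual cells and replace the two sentences that give N=180 and 0.66 with text along these lines:

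> After 10% drop-out we expect about 81 spouse/partner and 40 adult child/other family CGs per arm. At two-sided 0.017 and 80% power, the detectable group-vs-individual effect is [PASS result] in spouses/partners and [PASS result] in adult child/other family CGs. The detectable group-vs-individual by relationship type by time interaction is [PASS result].

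For each figure, state the SD or effect definition, the contrast tested and the arms included. Give the covariance structure and pattern of means as well, so that the Aim 1 and Aim 2 figures can be checked against each other.

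The cost is one PASS re-run and possibly a less favourable Aim 2 figure. No participants are added and the analysis model stays as it is.

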Thus, the extent to which CG interventions help to improve and strengthen CGs' social network structure and function and compensate for weak ties may help account for the positive impact of group interventions on CG wellbeing. In one of the few studies to compare a CG support intervention provided in either a group or individual format, Toseland and colleagues (1990) found that adult child CGs assigned to both intervention modalities experienced significant improvements in coping and reduced stress.¹¹ However, the processes, or mechanisms, by which adult child CGs improved differed across the two modalities; while CGs in the individually delivered program spent more time problem solving and discussing highly personal issues (e.g., marital difficulties), CGs in the group intervention were more likely to exchange information, share and compare caregiving experiences, and spend time engaging in social interactions and discussions that were non-caregiving related. Accordingly, CGs in the group intervention reported increases in the size of their social networks and greater positive changes in both formal and informal social support. *Individually-based interventions that are augmented with a group support component may not only lead to reduced CG burden and distress, but also may improve social network function and structure, both of which are essential for wellbeing and resilience in the caregiving role.*

An additional factor that is rarely taken into account in CG intervention trials is the extent to which various individual-level factors moderate the association between intervention group assignment and outcomes. For example, prior work has suggested that factors such as baseline CR symptom severity, CG distress, and ethnicity may impact enrollment, attrition rates and outcomes among CGs participating in CG interventions.^{30, 36} While studies typically control for these variables in a post-hoc fashion, few studies specifically sample or stratify results based on these potential moderators. By not accounting for important moderators a priori in the design phase, studies may lack the necessary power to detect moderators of intervention outcomes that can help determine for whom and under what circumstances varying intervention strategies are most effective. Identification of subgroups of patients who may

respond more favorably to different treatment strategies also can further help to tailor programs for maximum impact.

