- a) Individual Delivered TEP Arm:** Based on evaluation of the baseline interview, the CG and care manager will work together to determine which of the modules are most appropriate for the CG. In addition to two mandatory modules that cover the stages of dementia and provide a brief introduction to problem solving techniques, action plan development, and coping skills, CGs can select from a menu of additional modules covering various content areas evaluated during the course of the monthly assessments (e.g., communication skills, behavioral management techniques, stress management and coping skills, long-term planning, etc.). Each individual TEP session will begin with reviewing education related to the selected module. The remainder of each session will involve coaching the CG on emotion-focused and problem-focused coping strategies. The care manager will also discuss problem solving with the CG to reinforce the action plan and the educational component of the intervention. Each session will be delivered over the telephone and will last 40 minutes-1 hour. Sessions will occur approximately every other week, depending upon the availability and preference of the CG. The number of TEP contacts will depend on the number of topics chosen and covered.
- b) Group Delivered TEP Arm:** CGs assigned to this arm will be asked to participate in all TEP modules in a group format. Each call will take up to 1.5 hours. Each group will be comprised of 5-8 CGs who will call into a VANTS teleconference line at a pre-specified time. The content of the calls will mirror those in the individual TEP delivered program. As with the individual

TEP delivered program, each session will begin with reviewing a different education topic and the remainder of the call will involve reviewing weekly action plans, discussion of emotion and problem focused coping strategies, and skills training. This arm, however, will include the added component of peer group support. CGs will be given the option of sharing their contact information with one another. CGs will be asked to complete their workbooks prior to the next session.

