Outcomes: In order to analyze the degree to which randomization group is associated with changes in our three primary outcomes (i.e., CG distress in response to CR dementia-related symptoms, CG burden, and CG mental functioning) over time (Hyp 1A-1C), we will run three separate intent-to-treat, mixed effects linear regression models (using SAS PROC MIXED). Mixed models account for multiple observations and make use of all available data for each CG (regardless of drop-out or missing assessment periods), account for subject-level clustering, and accommodate modeling of contemporaneous and lagged effects and time variant and invariant variables. Specifications for the mixed models will include random effect estimates for intercept and slope (i.e., time) to account for within-individual variability. We will specifically test for group by time interactions. All models will control for baseline scores for the respective outcome and covariates identified during the preliminary analysis phase. It is important note that while these three variables are our primary outcomes, we also will run post-hoc mixed models (including mixed effects logistic models for binary outcomes; SAS PROC NLMIXED) to examine the relative impact of the intervention on other outcomes including CR frequency of NPI and RMBPC symptoms, CR IADL/ADLs, CG engagement in VA and non-VA services, and inpatient/outpatient costs (cost data will be analyzed using a Gamma distribution). Corrections will be made for multiple comparison effects.

Specific Aim 2-Evaluating the Moderating Role of CG-CR Relationship Type: In order to examine the moderating role of CG-CR relationship type on study/intervention engagement (Hyp 2A) and our 3 primary outcomes (Hyp 2B), we will again run the linear and logistic mixed effects models outlined above, and include estimation of random effects for both intercepts and slopes, as well as all main effects, relationship type*time interactions, and relationship type*randomization group*time interactions (i.e., all 2- and 3-way interactions). We also will run logistic regression models examining whether consent and engagement in each of the study arms for eligible CGs varies as a function of relationship type.

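### The Aim 1 model and power calculation ignore clustering within TEP call groups, so standard errors for hypotheses 1A and 1C may be too small

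*Combined protocol and SAP*

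**What the plan says.** Randomization is by individual caregiver, 135 per arm (L.2.2). Delivery then differs by arm. In the individual arm, TEP is given one-to-one by telephone. In the group arm (N.1.1.C.ii(b)), "Each group will be comprised of 5-8 CGs who will call into a VANTS teleconference line at a pre-specified time", and "This arm, however, will include the added component of peer group support". Members may also exchange contact details.

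For the three primary outcomes, the Aim 1 analysis in V.4.2 is a linear mixed model: "Specifications for the mixed models will include random effect estimates for intercept and slope (i.e., time) to account for within-individual variability". The test is of arm by time: "We will specifically test for group by time interactions". The same paragraph adds: "All models will control for baseline scores for the respective outcome and covariates identified during the preliminary analysis phase".

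The power calculation in V.4.1 uses a model that "considers the correlation among 4 repeated measures per CG", with 360 caregivers after dropout and a two-sided level of 0.017. It reports 80% power for a 0.4 effect "between the largest and smallest effects associated with intervention groups".

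No section gives a TEP-group effect, an ICC, a design effect or a cluster-robust standard error.

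**The concern.** The design is partially nested: caregivers in one arm share treatment groups, while those in the other two arms do not. A caregiver-level random intercept and slope are assumed independent from one caregiver to the next. They cannot absorb a change that members of the same call group have in common. Positive within-group correlation in the tested change therefore makes the group arm's mean change less precise than the model reports.

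The trial's own rationale makes such correlation plausible, though it does not size it. The Background argues that individual programs "augmented with a group support component may not only lead to reduced CG burden and distress", and burden and distress are the primary outcomes. If peers are an active ingredient, results may depend on which peers a caregiver is grouped with.

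Two of the three Aim 1 hypotheses involve this arm, and 1C is the comparison of delivery models named in the study purpose (H). At stake are confidence intervals that are too narrow, a type I error above 0.017, and a detectable effect larger than the same calculation gives without clustering. The 0.017 level is an allowance for three outcomes (0.05/3) and offers no protection against this.

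**Working it through.** **The plan's own figure.** The inputs from V.4.1 are 360 analysed (120 per arm), two-sided alpha 0.017 (z = 2.387), effect 0.4 and within-person correlation 0.75. The 80% cannot be uniquely reproduced, because the middle arm's position, the SD behind the 0.4 and the covariance form are not given.

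- Pairwise, SD 1: 0.4 × √(120/2) = 3.098; 3.098 − 2.387 = 0.711; power 76.2%.
- Three-arm F test (2 df): 80.6% if two arms are equal, 65.5% if the third lies midway.
- Pairwise on change, SD √(2 × (1 − 0.75)) = 0.707: about 98%.

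None of these readings includes TEP-group correlation. The loss of power is therefore given only in relative terms.

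**Cluster sizes.** 135/8 to 135/5 gives about 17-27 groups. With 10% dropout, mean analysed size m is 0.9 × 5 = 4.5 to 0.9 × 8 = 7.2; the middle case is 0.9 × 6.5 = 5.85.

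**Formulas.** Clustering is in one arm of the contrast only:

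- DE = 1 + (m − 1) × ICC
- r = √((DE + 1)/2), the ratio of correct to reported standard error; the detectable effect is multiplied by r
- type I error = 2 × (1 − Φ(2.387/r))
- effective n in the group arm = 120/DE

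The ICC is that of the tested change. It is an assumption.

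| ICC | m | DE | r | Type I error | Effective n |
|---|---|---|---|---|---|
| 0.01 | 4.5 | 1.035 | 1.009 | 0.018 | 116 |
| 0.05 | 5.85 | 1.2425 | 1.059 | 0.024 | 97 |
| 0.10 | 7.2 | 1.62 | 1.145 | 0.037 | 74 |

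**Check by simulation.** In 100,000 trials per setting (120 per arm; 27, 20 or 17 groups; t-test ignoring groups), type I error was 0.016-0.018 at ICC 0, 0.018 at 0.01, 0.022-0.027 at 0.05 and 0.027-0.037 at 0.10. A partially nested test (between-group mean square in the group arm, Satterthwaite degrees of freedom) gave 0.017-0.018 at every ICC from 0 to 0.10. A separate 40,000-trial run at m = 8 gave 0.027 (ICC 0.05) and 0.039-0.041 (ICC 0.10) for 1A and 1C. In that run 1B stayed at 0.016-0.018, and the 2-df arm-by-time test was also inflated (0.026 and 0.038).

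**Dependence on coding and duration.** A shared level that is constant over the analysed visits cancels from a slope. Whether that happens depends on whether baseline is an outcome or a covariate, on how time enters, and on how long the shared effect lasts after about 3 months of treatment. As an example, take linear time over months 0/3/6/12, where the sum of squared deviations of time is 78.75, and a shared effect of variance 0.05 present at all post-baseline visits:

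- the slope of (0, 1, 1, 1) is 5.25/78.75 = 0.0667, so shared slope variance is 0.05 × 0.0667² = 0.00022
- the rest is 0.25/78.75 = 0.00317
- the ICC is 0.00022/(0.00022 + 0.00317), about 0.065

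Simulated type I error with shared variance 5% of outcome variance at its peak (20,000 trials, Monte Carlo SE about 0.001, complete data, correlation 0.75):

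| Shared effect (weights at 0/3/6/12) | Linear time 0-12 | Linear time 3-12, baseline as covariate |
|---|---|---|
| Persisting (0, 1, 1, 1) | 0.024-0.029 | 0.017-0.018 |
| Growing (0, 0.25, 0.5, 1) | 0.027-0.040 | 0.023-0.027 |
| Fading (0, 1, 0.75, 0.5) | 0.018-0.019 | 0.019-0.022 |
| Gone by month 12 (0, 1, 0.5, 0) | 0.017-0.020 | 0.028-0.037 |

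With visits as categories over 0/3/6/12, the range across the four patterns is 0.021-0.033. At 1% shared variance, every setting gives 0.016-0.021.

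**The case against.** The strongest reply is that the size is not documented and may be trivial. The top figure needs ICC 0.10 with every group starting at 8. Four repeated measures and a slope in time suggest linear time over 0-12; if a shared effect fades after treatment, that coding gives only 0.017-0.020. This stands as a limit on the size. It does not remove the concern: V.4.1 and V.4.2 leave the coding open, and other equally admissible codings show inflation under the same fading patterns.

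The pattern simulation also gives caregivers no slope variance of their own, although V.4.2 plans a random slope. If such variance were half of the estimated-slope variance (an assumption), the persisting and growing ICCs over 0-12 fall to 0.034 and 0.052, and type I error to 0.020-0.023 and 0.022-0.027. This is correct, so the linear-time figures in the second table are upper-end. The first table fixes the ICC directly and is unaffected.

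Three further points stand:

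- The loss of power is less firm than the type I error. On the change-score reading, power stays near 92%-95% at ICC 0.10, and for the whole contrast the 240 caregivers fall only to 240/1.31, about 183, in the worst case.
- The nested test that was simulated used one change score per caregiver, so the behaviour of the full mixed model with 17-27 groups has not been shown.
- Care managers serve both active arms. Their correlation is a separate matter that could touch 1B and 1C and be hard to separate from TEP-group effects.

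Group membership could probably be rebuilt from contact logs and recordings, so a later sensitivity analysis would be possible. That supports the low cost of the fix; it is not a reason to leave the primary model without the term.

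**Conclusion.** The concern holds, in conditional form. The planned model treats group-arm caregivers as independent. If the tested change is correlated within TEP groups, reported precision for 1A and 1C is overstated. For an assumed ICC of 0.01-0.10, the correct standard error is 0.9%-14.5% larger than reported, type I error is 0.018-0.037 instead of 0.017, and the detectable effect is multiplied by 1.01-1.15. The middle case is 5.9%, 0.024 and 1.06. At ICC 0.01, or where the shared effect cancels from the slope, the consequence is negligible.

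Point estimates are not biased, TEP-group correlation does not affect 1B, and no size is claimed for Aim 2B. The plan should be amended because it neither says which case applies nor has a term that would adapt, and the remedy is cheap.

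**What to change.** 1. Record a TEP-group ID for each group-arm caregiver as groups form. Code those who never join a group as singleton clusters, so that all randomized caregivers stay in the intent-to-treat analysis.
2. In V.4.2, state whether baseline is an outcome or a covariate, and how time is coded.
3. For the three primary outcomes, specify a partially nested mixed model with a TEP-group random effect in the group-TEP arm only. Use a TEP-group slope or TEP-group-by-visit effect, plus a TEP-group intercept where post-baseline visits are the outcomes and it is estimable. Use Satterthwaite or Kenward-Roger degrees of freedom. Apply this model to 1A and 1C, and carry the term into Aim 2B.
4. In V.4.1, restate the Aim 1 detectable effect and power for contrasts involving the group arm over a stated ICC range, for example 0.01-0.10, without changing enrolment.

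The cost is SAP wording, one ID variable (care managers already log each contact) and an extra RANDOM statement in PROC MIXED. Enrolment, allocation and assessments do not change. If there is no clustering, the simulated nested test has about 56-85 instead of 238 degrees of freedom. Its critical value is 2.434-2.460 instead of 2.404, so intervals for 1A and 1C are about 1.3%-2.3% wider. Stated power becomes slightly less favourable. With about 17-27 groups, the variance component may be imprecise or estimated at zero.
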